1.3 DATA HANDLING CONVENTIONS

This section describes the rules and conventions used in the presentation and analysis of data.

In the statistical appendices and in-text tables, the following cohort label and group label will be used:

- Cohort label:
 - AD patients
 - Healthy volunteers
- Group label:
 - AD patients – lesional skin
 - AD patients – non-lesional skin
 - HV – healthy skin

For parameters with evaluations before administration and in cases of rechecked value(s) for one subject, only the last observation will be used as baseline in descriptive statistics and derivations of other parameter values. After baseline, only observations planned in the protocol will be used in descriptive statistics.

If not otherwise stated in the statistical section of the protocol:

- Missing TEWL data (including data from visits excluded of the efficacy analyses after the use of prohibited medication) will be imputed using Last Observation Carried Forward (LOCF) imputation ; sensitivity analyses will be performed to assess the precision of LOCF imputation versus MMRM imputation.
- Descriptive statistics for quantitative parameters will be provided using number of observations (N), mean, standard deviation (SD), standard error of the mean (SEM), minimum, maximum and median.
- Descriptive statistics for qualitative parameters will be provided using frequencies (N) and percent (%).

Handling missing data for adverse events

In case of missing or inconsistent information on the time of onset, an AE will be counted as a treatment-emergent adverse event (TEAE) unless it can clearly be ruled out that it is not a TEAE (eg, by partial dates or other information).

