Lesional and non-lesional skin areas for TEWL assessment and STS will be identified on the upper limbs or lower limbs at baseline ("predefined skin area"). TEWL and STS-assessment at pre-defined non-lesional (normal looking) skin area in AD patients should be made about 4 cm from the edge of the lesional area.

Within the predefined lesional skin (LS) and non-lesional skin (non-LS) areas three closely adjacent spots will be identified for subsequent skin barrier function assessment (3 spots on lesional skin, 3 spots on non-lesional skin). These spots must not overlap with each other once skin tapes are applied.

The skin barrier function without and before STS will be assessed using TEWL measurement on each of the three spots within these pre-defined skin areas at each visit.

Repeated TEWL assessment in pre-defined lesional and non-lesional skin areas of AD patients after STS for lipidomics, proteomics and transcriptomics analysis in STS samples will be conducted at baseline (Week 0, Day 1), Week 2 (Day 15), Week 4 (Day 29), Week 8 (Day 57), Week, 12 (Day 85), and at EoT at Week 16 (Day 113).

In order to allow the skin to recover from the STS, the skin barrier function assessment with STS will be performed as follows: STS assessment on baseline (Week 0), Week 8 and Week 16 will be conducted on the first spot within the predefined lesional and non-lesional skin area. STS assessment on Week 2 will be conducted on the second spot. STS assessment on Week 4 and Week 12 will be conducted on the third spot.

TEWL will be measured before and after 5, 10, 15, and 20 STS (5 TEWL assessments per visit) on targeted, predefined lesional, non-lesional skin in AD patients at baseline, Week 2, Week 4, Week 8, Week 12, and Week 16 on the predefined first, second or third spot, respectively.

Skin barrier function in approximately twenty healthy volunteers matched for age, gender, location of targeted lesion area, and study site to the AD cases will be assessed in a similar manner at baseline, twice a week during the first two weeks, once a week during Week 3 to Week 4, every two weeks from Week 4 to Week 8, and every four weeks up to Week 16 thereafter, serving as a reference comparator for skin barrier function.

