9.2 SAMPLE SIZE DETERMINATION

Sample size for this exploratory study was based on medical/clinical judgement and is consistent with the sample size from similar studies in the literature (1). No formal sample size calculation was performed. TEWL data collected in similar settings as planned for this study were not available: ie, TEWL values after 5 skin tape strips, and pre- and post-dupilumab treatment are unknown.

Allowing for drop-out rate of 15%, a total of approximately 24 patients with moderate to severe AD will be enrolled to achieve 20 evaluable patients: ie, patients with no major or critical deviations related to IMP and/or TEWL measurements, for whom the TEWL data for primary analysis: ie, TEWL at baseline and Week16, are considered sufficient and interpretable. An approximately equal number of age, gender, location of targeted lesion area and site matched healthy volunteers serving as a reference comparator cohort will be enrolled. Drop-out rate in healthy volunteers is expected to be zero. Any drop-out healthy volunteer for whom the matched patient is considered as evaluable will not be replaced.

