9.4.7.1 Description of efficacy variables

Efficacy parameters are described in [Section 8.2](#). The derivation of baseline results is described in [Section 9.4.4.2](#).

The analysis of the efficacy marker will be based on the mITT population. As a sensitivity analysis, the primary endpoint will also be analyzed based on the ITT population. Secondary endpoints analysis might be run on the ITT population as sensitivity analysis in case an important number of patients using rescue therapy is observed.

Sub-analysis might be done for adolescents and adults, if deemed appropriate.

TEWL data collected at the same visit from without and before STS measurement on each of the three spots within the predefined skin areas will be averaged, unless a large difference between spots is observed.

Analysis

Table 4 - Efficacy analyses

Endpoint	Statistical Analysis Methods
Primary	
Percent change from baseline in TEWL after 5 STS assessed on lesional skin at Week 16 in AD patients	
Raw data and change from baseline; ie, absolute and percentage changes, will be summarized with descriptive statistics (such as mean, median, SD, minimum, and maximum) based on the mITT and ITT populations.
 
Profiles for baseline and Week 16 time points will be generated for individual values: eg, spaghetti plot and boxplot, and patients' cohort means.
 
For information purpose as study is not powered (no multiplicity correction will be applied):
 
Difference between baseline and Week 16 values will be tested through one-sided paired t-test at a Type 1 error level of alpha=0.05 ($H_0: 0 \leq TEWL_{Week16} - TEWL_{baseline}$, $H_a: 0 > TEWL_{Week16} - TEWL_{baseline}$).
 
Point estimate, two-sided 90% confidence interval and corresponding one-sided p-value will be reported.
 
If assumption of normal distribution is strongly violated, non-parametric methods: eg, Wilcoxon signed-rank test, will be used; normality assumption will be assessed through quantile-quantile plot and Shapiro-Wilk test at 5% Type I error.

Endpoint	Statistical Analysis Methods
Secondary	
Change (percent and absolute) from baseline in TEWL after 20 STS assessed on lesional skin at Week 16 in AD patients	The similar approach as for the analysis of primary endpoint will be used.

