1.2 MODIFICATIONS FROM THE STATISTICAL SECTION OF THE PROTOCOL

This section describes the modifications and additional statistical analyses from the protocol.

Due to unbalance between adults and adolescents atopic dermatitis (AD) patients, analyses based on age group (adult/adolescent) will only be performed for adverse event (AE) data reporting.

The study objectives are exploratory. Sample size was not based on power requirements. No multiplicity correction will be used for the tests performed as part of the statistical analyses.

Analysis population

Any participant with major deviation impacting assessment of efficacy data (except for deviations concerning AD related prohibited therapy administration) will be excluded for the modified-Intent-to-treat (mITT) population.

Demographic and medication data

Descriptive statistics for disease duration since AD diagnostic will be provided by cohort and age group (adults/adolescents).

Medications (including rescue medications) administered during the follow-up period will be summarized, in addition to previous and concomitant medications.

Efficacy analysis

Change from baseline in TEWL data is defined as change versus Day 1 TEWL data at matched number of STS samples (eg, TEWL after 5 STS at Week 16 will be compared to TEWL after 5 STS at Day 1).

Individual Signs Score (ISS) questionnaire was not done as planned per protocol. Instead, to assess lesion severity locally, Quantificare evaluation data will be used. Global Individual Signs Score (GISS) was evaluated during the study. Both Quantificare data and GISS data will be analyzed using descriptive statistics for raw data, absolute and percent by timepoints. For AD patients, on mITT population, correlation with TEWL data will be evaluated. Scatterplots will be provided to visualize the form of the relationship and Spearman's rank correlation coefficient as well as p-values at specific timepoints (Baseline, Week 8 and Week 16) will be provided.

Adverse event data

All summary of AEs will be provided by cohort and age group.

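### Where SAP 1.3 applies LOCF to after-strip TEWL, a missing Week 16 value can be filled from earlier in treatment and from another skin spot, and the rule is not reconciled with the protocol's no-imputation default

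*SAP*

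**What the plan says.** The primary endpoint in Protocol Table 4 (Section 9.4.7.1) is "Percent change from baseline in TEWL after 5 STS assessed on lesional skin at Week 16 in AD patients". The difference "will be tested through one-sided paired t-test at a Type 1 error level of alpha=0.05", and "Point estimate, two-sided 90% confidence interval and corresponding one-sided p-value will be reported". SAP 1.2 fixes the comparison at the same number of strips: "TEWL after 5 STS at Week 16 will be compared to TEWL after 5 STS at Day 1".

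After-strip TEWL is read only on the spot that is stripped at that visit (Protocol 8.2.1.1 and the Section 1.3 footnotes). The Synopsis assigns Day 1, Week 8 and Week 16 to the first spot and Week 2 to the second, and states that "STS assessment on Week 4 and Week 12 will be conducted on the third spot". The Day 1 to Week 16 contrast is therefore within one spot by design.

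On missing data:

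- **Protocol 9.4.7:** missing efficacy data are not imputed. The exception is visit values removed because of rescue, which are imputed if many patients use rescue, by a method left to an SAP.
- **SAP 1.3:** missing TEWL is filled by LOCF, including visits excluded after prohibited medication, and "sensitivity analyses will be performed to assess the precision of LOCF imputation versus MMRM imputation". The rule is introduced as applying only where the protocol's statistical section does not state otherwise.
- **SAP 1.2:** the list of modifications to the protocol does not mention LOCF.

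**The concern.** Two things are wrong. First, the scope of LOCF is undecided. The SAP rule defers to a protocol section that says the opposite for ordinary missing data, so two analysts could produce different primary results from the same plan.

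Second, LOCF suits this measurement poorly wherever it is used. The trial measures how the barrier changes over 16 weeks, and LOCF assumes no change after the last reading. For after-strip TEWL and TEWL AUC it can also place a second- or third-spot reading in a first-spot contrast. There is no patient control arm (Protocol 6.3), so any bias goes straight into the estimate. Drop-out is expected to be zero in healthy volunteers (Protocol 9.2), so carried values would fall mainly on the patient side of the ratio to that cohort.

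MMRM analyses incomplete data without filling them in. Calling it imputation, and calling the comparison a test of LOCF's precision, leaves open what will be run. No model is given.

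**Working it through.** **1. The plan's own figure.** Protocol 9.2 gives 20 evaluable patients and 15% drop-out: 20 / (1 - 0.15) = 23.5, rounded up to 24, as stated. The difference, 24 - 20 = 4 (4/24 = 16.7%), serves below as the number of missing Week 16 values. This is a working figure: patients can be non-evaluable for other reasons, and patients who stop drug stay in for TEWL (Protocol 7.1.1).

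**2. Where a carried Week 16 value comes from** (Synopsis schedule):

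| Last reading | Spot | Weeks since that spot was last stripped | Weeks before Week 16 |
|---|---|---|---|
| Week 2 | second | not stripped before | 14 |
| Week 4 | third | not stripped before | 12 |
| Week 8 | first | 8 | 8 |
| Week 12 | third | 8 | 4 |
| (Week 16 itself) | first | 8 | 0 |

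Three of the four scheduled sources are on another spot. All four are earlier in treatment. Before-strip TEWL is read on all three spots and averaged, so the spot problem does not arise there.

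**3. Bias.** Understatement = (number carried / n) x mean gap, where the gap is the share of the Week 16 effect not yet reached at the source visit. The documents give no effect or SD; Protocol 9.2 says that "TEWL values after 5 skin tape strips, and pre- and post-dupilumab treatment are unknown". Assume the last reading is equally likely at Weeks 2, 4, 8 and 12, and that these shares have been reached:

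- Faster curve 40/60/85/95%: mean 70%, gap 30%.
- Slower curve 25/40/65/85%: mean 53.75%, gap 46.25%.

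With 4 carried: 4/24 x 30% = 5.0% and 4/24 x 46.25% = 7.7%. With 7 carried (30% of 24 is 7.2): 7/24 x 30% = 8.8% and 7/24 x 46.25% = 13.5%. If all 4 come from Week 12: 4/24 x 5% = 0.8% and 4/24 x 15% = 2.5%, or zero if the effect has fully levelled off.

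**4. A second set of assumptions, in percentage points.** One value each is carried from Weeks 2, 4, 8 and 12. Mean changes at Weeks 2/4/8/12/16:

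- -20/-30/-40/-45/-45%: mean carried value -33.75, gap 11.25, bias 4/24 x 11.25 = 1.9 points. Simulated: 1.8 to 2.3.
- -10/-20/-30/-38/-48%: mean carried value -24.5, gap 23.5, bias 4/24 x 23.5 = 3.9 points. Simulated: 3.8 to 4.2.

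Worst case, all 4 from Week 2 on the second curve: 4/24 x 38 = 6.3 points, with coverage of the 90% CI about 77%.

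**5. Interval.** Half-width = t(0.95, n-1) x SD / sqrt(n). For n = 24: 1.714 / 4.899 = 0.350 SD. For n = 20: 1.729 / 4.472 = 0.387 SD. Treating carried values as observed narrows the interval by 1 - 0.350/0.387, about 9.5%, at equal SD.

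Simulated coverage of the nominal 90% CI used the step 3 curves, n = 24, a true log change of -0.40, patient SD of the effect 0.25, residual SD 0.15, between-spot SD 0 or 0.15, and random missingness:

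- LOCF, 15% missing: about 88-89%.
- LOCF, 30% missing: about 80-86%.
- Observed pairs: 89-91%, with no bias.

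A repeat with 6,000 runs per setting agreed to within about one point (87-88% and 80-87% for LOCF). A 10% mean difference between the first and the other spots, on the faster curve, spreads the understatement to 2-8% at 15% missing and 2-14% at 30%.

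**6. Why the MMRM wording matters.** Under the step 4 assumptions, an MMRM-type mean was within 0.5 points of the truth. Filling in its predictions and analysing them as observed gave only 84-90% coverage.

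**The case against.** The strongest reply is that the protocol already settles the matter. Read literally, the SAP rule yields to Protocol 9.4.7, so ordinary drop-outs are not carried forward and LOCF supplies only the method for rescue-removed visits. This limits how often LOCF would be used, but does not remove the point. SAP 1.3 speaks of missing TEWL in general, the protocol's trigger (many rescue users) has no threshold, and LOCF is the only method offered when it is met.

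Other replies carry weight:

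- Week 2, 4 and 12 after-strip changes already cross spots by design, the spots are adjacent, and no document gives a between-spot difference.
- At 15% missing the effect is modest. Root mean squared error was about equal (0.065-0.075 for LOCF, 0.067-0.071 for MMRM). LOCF was clearly worse only at 30% missing with the slower curve (about 0.087-0.088 against 0.074-0.080).
- MMRM needs data missing at random and a covariance model that 24 patients can support. Visit and spot are confounded, so visit means absorb an average spot difference but not a patient's own.
- An MMRM comparison and an ITT sensitivity analysis are already planned. The test is informational, and "No formal sample size calculation was performed".

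A reader might infer more than the documents support:

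- **Every carried value comes from another spot.** Week 8 is the first spot.
- **The source spot has recovered less from stripping.** Each scheduled source has had the same 8 weeks or was never stripped; it is only earlier in treatment.
- **The SAP states that carried values count as observations.** It does not. That is the natural inference, because no flag or adjustment is described.

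**Conclusion.** The point holds in a bounded form. SAP 1.3 and Protocol 9.4.7 leave the use of LOCF undecided. Wherever it is applied to after-strip TEWL or TEWL AUC, it can bring earlier-treatment and other-spot readings into a same-spot contrast, with no stated adjustment to the test or interval.

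The sizes in steps 3 to 5 rest wholly on assumed curves, variances and missingness. They show a modest understatement at the stated drop-out and a clearer one if rescue-removed visits raise the missing share toward 30%. The plan should be changed, but the consequence is limited to the Week 16 estimate, its 90% CI and the time course. No confirmatory decision depends on them.

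**What to change.** 1. Reconcile SAP 1.3 with Protocol 9.4.7. State which missing values, if any, are imputed, and list any departure in SAP 1.2.
2. Make the Table 4 paired analysis on observed first-spot Day 1/Week 16 pairs the main result, as the protocol's default implies.
3. Add an MMRM on observed changes from Day 1, with no imputed data, as the main missing-data analysis, also covering rescue-removed visits. Specify visit as a factor, the baseline covariate, the covariance structure with a simpler fallback (unstructured over five post-baseline strip visits needs 5 x 6 / 2 = 15 parameters), and how post-rescue visits enter the analysis.
4. Keep LOCF only as a sensitivity analysis, not carried across spots for after-strip TEWL or AUC. State whether premature end-of-treatment strips count as a source: they are done on the longest-rested spot, and the SAP is silent on carrying them.
5. Report numbers observed and carried, with source visit.
6. Delete the wording that treats MMRM as imputation and the comparison as a check of LOCF's precision.

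The cost is SAP text and a somewhat wider interval. At equal SD, 20 observed pairs give a half-width of 0.387 SD against 0.350 SD for 24 values, about 10% wider. Observed pairs also need missingness unrelated to outcome, which is why the MMRM should stand beside them.

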2 SOFTWARE DOCUMENTATION

The analysis of clinical data will be performed under the responsibility of Sanofi Biostatistics Department, using SAS[®] (SAS Institute, NC USA).

3 LIST OF APPENDICES

3.1 POTENTIALLY CLINICALLY SIGNIFICANT ABNORMALITIES CRITERIA – ADULT HEALTHY VOLUNTEERS

CRITERIA for POTENTIALLY CLINICALLY SIGNIFICANT ABNORMALITIES For Studies in healthy subjects only		
Parameter	PCSA	Comments
Vital signs		
HR	≤40 bpm and decrease from baseline ≥20 bpm ≥100 bpm and increase from baseline ≥20 bpm	To be applied for all positions (including missing) except STANDING.
SBP	≤95 mmHg and decrease from baseline ≥20 mmHg ≥140 mmHg and increase from baseline ≥20 mmHg	To be applied for all positions (including missing) except STANDING.
DBP	≤45 mmHg and decrease from baseline ≥10 mmHg ≥90 mmHg and increase from baseline ≥10 mmHg	To be applied for all positions (including missing) except STANDING.
Orthostatic Hypotension		-
Orthostatic SBP	≤-20 mmHg	
Orthostatic DBP	≤-10 mmHg	
Weight	≥5% increase from baseline ≥5% decrease from baseline	FDA Feb 2007.

3.2 POTENTIALLY CLINICALLY SIGNIFICANT ABNORMALITIES CRITERIA – ADULT ATOPIC DERMATITIS PATIENTS

CRITERIA for POTENTIALLY CLINICALLY SIGNIFICANT ABNORMALITIES for phase 2/3 studies (oncology excepted)		
Parameter	PCSA	Comments
Vital signs		
HR	≤50 bpm and decrease from baseline ≥20 bpm ≥120 bpm and increase from baseline ≥20 bpm	To be applied for all positions (including missing) except STANDING.
SBP	≤95 mmHg and decrease from baseline ≥20 mmHg ≥160 mmHg and increase from baseline ≥20 mmHg	To be applied for all positions (including missing) except STANDING.
DBP	≤45 mmHg and decrease from baseline ≥10 mmHg ≥110 mmHg and increase from baseline ≥10 mmHg	To be applied for all positions (including missing) except STANDING.
Orthostatic Hypotension		
Orthostatic SDB	≤-20 mmHg	
Orthostatic DBP	≤-10 mmHg	
Weight	≥5% increase from baseline ≥5% decrease from baseline	FDA Feb 2007.

3.3 POTENTIALLY CLINICALLY SIGNIFICANT ABNORMALITIES CRITERIA – MINOR PARTICIPANTS

CRITERIA for POTENTIALLY CLINICALLY SIGNIFICANT ABNORMALITIES For Studies in Children			
Parameter	Age range	PCSA	Comments
Vital Signs			Ref. : Kidney Disease Outcomes Quality Initiatives (KDOQI) Guideline 13; 1996; The fourth report on the diagnosis, evaluation, and treatment of high blood pressure in children and adolescents, Pediatrics 2004; Bowman E & Fraser S Neonatal Handbook 2012; Mulberg AE et al. Pediatric Drug Development Concepts and applications. John Wiley & sons, Inc. 2009; Pediatric respiratory rates http://www.health.ny.gov/
SBP	Birth/0 to 27 days old (Neonates)	≤60 mmHg and decrease from baseline ≥20 mmHg ≥85 mHg and increase from baseline ≥20 mmHg	Based on definition of Hypertension as average SBP or DBP ≥95 th percentile for gender, age, and height on ≥3 occasions
	28 days/1 month to 23 months old (Infants)	≤70 mmHg and decrease from baseline ≥20 mmHg ≥98 mmHg and increase from baseline ≥20 mmHg	
	24 months/2 years to <6 years old (Children)	≤70 mmHg and decrease from baseline ≥20 mmHg ≥101 mHg and increase from baseline ≥20 mmHg	
	6 to <12 years old (Children)	≤80 mmHg and decrease from baseline ≥20 mmHg ≥108 mmHg and increase from baseline ≥20 mmHg	
	12 to 16/18 years old (Adolescents)	≤90 mmHg and decrease from baseline ≥20 mmHg ≥119 mmHg and increase from baseline ≥20 mmHg	
DBP	Birth/0 to 27 days old (Neonates)	≤34 mmHg and decrease from baseline ≥10 mmHg ≥50 mHg and increase from baseline ≥10 mmHg	
	28 days/1 month to 23 months old (Infants)	≤34 mmHg and decrease from baseline ≥10 mmHg ≥54 mHg and increase from baseline ≥10 mmHg	

**CRITERIA for POTENTIALLY CLINICALLY SIGNIFICANT ABNORMALITIES
For Studies in Children**

Parameter	Age range	PCSA	Comments
	24 months/2 years to <6 years old (Children)	≤34 mmHg and decrease from baseline ≥10 mmHg ≥59 mHg and increase from baseline ≥10 mmHg	
	6 to <12 years old (Children)	≤48 mmHg and decrease from baseline ≥10 mmHg ≥72 mHg and increase from baseline ≥10 mmHg	
	12 to 16/18 years old (Adolescents)	≤54 mmHg and decrease from baseline ≥10 mmHg ≥78 mHg and increase from baseline ≥10 mmHg	
Orthostatic hypotension	All age ranges	SBP: St — Su ≤- 20 mmHg DBP: St — Su ≤- 10 mmHg	
Temperature	All age ranges	Rectal, ear or temporal artery: ≥100.4 °F/38.0 °C Oral or pacifier: ≥99.5 °F/37.5 °C Axillary or skin infrared: ≥99 °F/37.2 °C	Ear temperature not accurate below 6 months of age
Respiratory rate	Birth/0 to 27 days old (Neonates)	<30 per minutes >60 per minutes	Based on normal range
	28 days/1 month to 23 months old (Infants)	<24 per minutes >40 per minutes	
	24 months/2 years to <6 years old (Children)	<22 per minutes >34 per minutes	
	6 to <12 years old (Children)	<18 per minutes >30 per minutes	
	12 to 16/18 years old (Adolescents)	<12 per minutes >20 per minutes	
SaO2	All age ranges	≤95 %	
Weight	All ranges	≥5 % weight loss from baseline	Based on identification of trends in the child's growth with a series of visits WHO Multicentre Reference Study Group, 2006; Center for Disease Control. Growth chart 2007
